#### **8.6.2.2. As-Treated Analysis**

The primary analysis of efficacy includes all eGFR values collected during trial follow-up through Week 48, regardless of patient receiving study drug. The as-treated sensitivity analysis to assess the treatment effect while receiving study drug is based on the ITT population, but excludes any eGFR values collected after final dose. The as-treated analysis is performed using the MMRM statistical model defined in Section 8.6.1, with eGFR values collected after final dose treated as missing. Missing data are not imputed for the as-treated sensitivity analysis.

#### **8.6.2.3. Per-Protocol Population Analysis**

The per-protocol population analysis is performed for the per-protocol population (Year 1) using the MMRM statistical model defined in Section 8.6.1. Missing data will not be imputed for the per-protocol population sensitivity analysis.

### **8.7. Year 1: Key Secondary Endpoint**

#### **8.7.1. Primary Analysis of Year 1 Key Secondary Endpoint**

The Year 1 key secondary endpoint of this study is the change in eGFR at Week 52 (i.e., 4 weeks following the last dose after one year of drug exposure). Analysis of Week 52 assesses the preserved drug benefit (relative to placebo) following withdrawal of treatment; therefore, analysis of Week 52 data does not include the eGFR values collected during treatment.

The change from baseline eGFR at Week 52 for patients treated with bardoxolone methyl is compared to placebo using an analysis of covariance (ANCOVA) model, with BASE\_eGFR,

ACR\_STRAT, and TRT\_EXP1 as covariates, and TRT as the fixed effect. Inclusion of the fraction of expected one-year exposure to treatment (TRT\_EXP1; Section 6.5.11) in the ANCOVA model as a covariate provides an adjustment for eGFR values collected from early discontinuation patients having follow-up collected after less than 1-year of drug exposure.

The ANCOVA analysis uses eGFR values collected in the Week 52 analysis window (Section 6.5.4), which includes the follow-up assessment for patients who discontinued treatment early in the first year. Missing Week 52 eGFR data are imputed as defined in Section 8.5.3 using standard imputation.

The difference between bardoxolone methyl and placebo in change from baseline of eGFR is estimated along with the 95% confidence interval at Week 52.

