#### 4.3.1. Primary Endpoints

With 157 patients enrolled (78 in one group and 79 in the second group), the study will have approximately 80% power to detect a difference between the two treatment groups in change from baseline in eGFR of 3.4 mL/min/1.73 m^2 for the primary endpoint at Week 48 in Year 1. The power calculation for Year 1, which was based on mixed-model repeated measures (MMRM) analysis, assumes the following:

- 9 repeated measurements (Weeks 1, 2, 4, 6, 8, 12, 24, 36, and 48) having compound symmetry covariance structure
- The correlation between observations on the same subject is 0.7
- Two-sided Type I error rate of 0.025
- Standard deviation of change from baseline in eGFR of 8 mL/min/1.73 m^2
- Analyses at Week 48 are based on the intent-to-treat (ITT) population

Analysis of the Year 2 primary endpoint, which also will use the ITT population, will have approximately 80% power to detect a difference of 3.3 mL/min/1.73 m^2 assuming 13 repeated measurements, a correlation of 0.7 between observations, a standard deviation of 8 mL/min/1.73 m^2, and a two-sided type I error rate of 0.025. The primary analysis of efficacy will use an unstructured covariance structure, which is expected to have approximately the same power as the analysis with compound symmetry used for study planning.

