#### 4.3.2. Key Secondary Endpoint

With 157 patients enrolled, the study will have a minimum detectable difference (i.e., 50% power) between the two treatment groups in change from baseline in eGFR of approximately 2.9 mL/min/1.73 m^2, and 80% power to detect a difference of 4.0 mL/min/1.73 m^2 for the key secondary endpoint at Year 1 and at Year 2. The power calculation, which was based on a 2-sample t-test as an estimate for the planned ANCOVA analysis, assumes the following:

- Two-sided Type I error rate of 0.025 for Year 1 and 0.025 for Year 2
- Standard deviation of change from baseline in eGFR of 8 mL/min/1.73 m^2
- Multiple imputation is used for missing data
- Analyses of the key secondary endpoint are based on the ITT population

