### **8.5.3. Missing eGFR for ANCOVA Analyses**

Missing eGFR data are imputed using multiple imputation for the primary analysis of eGFR where the analysis method is defined as ANCOVA (i.e., Week 52 and Week 104) (Section 6.6.1.2). For the primary analysis, multiple imputation is based on the treatment group to which the subject is assigned. A tipping point analysis is used to assess the validity of the MAR assumption.

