## **8.9. Year 2: Key Secondary Endpoint**

### **8.9.1. Primary Analysis of the Year 2 Key Secondary Endpoint**

The Year 2 key secondary endpoint of this study is the change in eGFR at Week 104 (i.e., 4-weeks following the last dose after two years of drug exposure). Analysis of Week 104 assesses for retained drug benefit (relative to placebo) following withdrawal of treatment; therefore, the analysis of Week 104 data does not include eGFR values collected during treatment.

The change from baseline eGFR at Week 104 for patients treated with bardoxolone methyl are compared with placebo in a manner similar to the ANCOVA analysis of Week 52 in Year 1 (Section 8.7.1) with the following modification:

- TRT\_EXP2 is added as a covariate and TRT\_EXP1 is removed

The analysis uses eGFR values collected in the Week 104 analysis window (Section 6.5.4), which includes the follow-up assessment for patients who discontinued treatment early in the second year. Discontinuing treatment in the second year requires that patients received at least one dose of study drug in the second year. Missing Week 104 eGFR data are imputed as described in Section 8.5.3.

The difference between bardoxolone methyl and placebo in change from baseline of eGFR are estimated along with the 95% confidence interval at Week 104.

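### As written, missing Week 52 and Week 104 eGFR is imputed from the assigned arm alone; the SAP should list the imputation predictors and include the patient's earlier eGFR

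*SAP*

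**What the plan says.** SAP 8.7.1 (Week 52) separates off-treatment from on-treatment data: "therefore, analysis of Week 52 data does not include the eGFR values collected during treatment". SAP 8.9.1 does the same for Year 2: "the analysis of Week 104 data does not include eGFR values collected during treatment". The ANCOVA adjusts for baseline eGFR, ACR stratum and the exposure fraction (TRT_EXP1 or TRT_EXP2).

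Missing Week 52 and Week 104 values are multiply imputed under missing at random (SAP 6.6.1.2). On the model itself, SAP 8.5.3 says only: "For the primary analysis, multiple imputation is based on the treatment group to which the subject is assigned". Section 8.7.1 adds that imputation is standard. No section lists predictors. Sections 8, 8.6 and 8.8 refer to separate documents for further detail and pseudo-code, which are not among the documents available here.

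The sensitivity analyses give indirect evidence:

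- The Week 48 tipping-point analysis (8.6.2.1) starts with a step that makes missingness monotone, which implies imputing across visits. The Week 52 version (8.7.2.1) has no such step.
- Control-based imputation for Week 52 (8.7.2.2) names only Week 52 placebo data as its source.

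Three rules turn values into missing ones whatever the patient's attendance: eGFR after dialysis or transplant (SAP section 6), Week 104 for anyone not dispensed Year 2 drug (SAP Table 3, note g, kept in addendum Table 4, note a), and eGFR after a COVID-19 diagnosis (addendum 4.5).

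**The concern.** If imputation uses the arm alone, or the arm plus the ANCOVA covariates, a patient whose eGFR fell steadily before the endpoint was lost is imputed like any other patient in that arm with the same covariates. The Week 48 and Week 100 MMRM do use that history. The same label, missing at random, therefore means less in the MMRM than in the ANCOVA: there, loss may depend on the patient's own earlier eGFR, and here it may not.

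The rule-based gaps make this more than a formality. Patients who reach dialysis or transplant plausibly had low eGFR. Patients who stopped in Year 1 are asked to keep attending, and their later eGFR enters the Week 100 MMRM, yet a literal Week 104 imputation would not draw on it.

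Week 52 and Week 104 each have a place in an alpha-controlled sequence (SAP 8.4), and SAP 2.1 makes the off-treatment comparison the main purpose of the trial.

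**Working it through.** **Inputs from the SAP.** 78 and 79 patients (4.3.1). For the key secondary endpoints (4.3.2): "Standard deviation of change from baseline in eGFR of 8" mL/min/1.73 m²; "Two-sided Type I error rate of 0.025 for Year 1 and 0.025 for Year 2"; power "which was based on a 2-sample t-test as an estimate for the planned ANCOVA analysis". A correlation of 0.7 is stated in 4.3.1, for the MMRM visits only.

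**Assumptions, because the documents give no figure.** Missing rate m of 10–20%; correlation ρ = 0.7 between on- and off-treatment change; log-odds of loss −0.10 per mL/min, that is −0.8 per SD of 8.

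**1. The plan's own figures.** SE = 8 × √(1/78 + 1/79) = 1.277. The critical t (155 df, two-sided 0.025) is 2.263. The 50%-power difference is 2.263 × 1.277 = 2.89 (stated 2.9). The noncentral t gives 3.97 at 80% power, and 80.7% power at 4.0 (stated: "80% power to detect a difference of 4.0"). Both figures reproduce, and both count all 157 patients as fully informative.

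**2. What arm-based imputation adds.** When only the outcome is missing, drawing it from the arm, or from the arm and the ANCOVA covariates, returns the regression already fitted to the observed patients, plus noise. A simulation (800 trials, 20 imputations, Rubin's rules, ANCOVA on treatment and baseline) confirms this. In every scenario, imputation by arm plus baseline differed from complete cases by at most 0.004 on average. At 10% missing its mean SE was 1.357, against 1.349 for complete cases.

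**3. Bias when low eGFR drives loss only in the bardoxolone arm.** Bias = ρ × SD × d, where d is the mean standardised on-treatment change among bardoxolone patients still observed. Integrating the logistic model over a standard normal gives d:

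| Missing | d | Bias = 0.7 × 8 × d |
|---|---|---|
| 10% | 0.075 | 0.42 |
| 15% | 0.111 | 0.62 |
| 20% | 0.145 | 0.81 |

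Other patterns:

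- Loss unrelated to eGFR, or the same mechanism at the same rate in both arms: about 0 (simulated −0.01 and −0.02).
- The same mechanism but 10% missing in one arm and 20% in the other: 5.6 × (0.145 − 0.075) ≈ 0.4, with the sign set by which arm loses more.
- Steeper slope (−1 per SD, bardoxolone only), 10% placebo and 20% bardoxolone missing: simulated +0.9 to +1.0. Rejection under the null at nominal 0.025 was 0.050, against 0.013 with on-treatment eGFR as a predictor (Monte Carlo SE about √(0.025 × 0.975/800) = 0.006).
- The same slope with ρ = 0.5 and 5% versus 15% missing: bias +0.5, null rejection 0.025, so no visible inflation.
- Opposite mechanisms in the two arms: −1.4.

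In all the simulated patterns, adding the on-treatment value left a residual bias of at most 0.08.

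**4. Precision under random loss.** The variance factor is 1/(1 − m) without the predictor and (1 − ρ²m)/(1 − m) with it, so the SE ratio is 1/√(1 − 0.49m).

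| Missing | SE ratio | 80%-power difference, without | with |
|---|---|---|---|
| 10% | 1.025 | 4.18 | 4.08 |
| 15% | 1.039 | 4.31 | 4.14 |
| 20% | 1.053 | 4.44 | 4.21 |

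At 20% missing, the figure with the predictor is 4.33 for ρ = 0.5 and 4.06 for ρ = 0.9.

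**The case against.** A reader might infer that the SAP forbids on-treatment eGFR in the imputation. It does not. The sentences in 8.7.1 and 8.9.1 say which values are analysed, and the sentence in 8.5.3 can be read as naming the donor arm, in contrast to control-based imputation. The pseudo-code is elsewhere and may already list earlier visits. This stands: the exclusion is a reading of the text, not a stated rule.

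The correlation of 0.7 belongs to the MMRM visits, and SAP 12.1 expects off-treatment values to correlate differently. This also stands, so 0.7 is an assumption here. Section 12.1, however, argues against modelling both kinds of value in one MMRM. A within-arm imputation regression estimates the relation freely and makes no on-treatment value an outcome.

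Many early stoppers are not missing. The Week 52 window runs from last dose, a follow-up visit four weeks after early termination is requested (SAP Table 2, note k), and the addendum removes the upper bound of the Week 104 window. That lowers the missing rate, but it does not help where values are missing by rule.

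The tipping-point analysis covers part of this ground. The biases above correspond to bardoxolone patients being imputed about 4 mL/min too high (0.42/0.10, 0.62/0.15, 0.81/0.20), and 1-point shifts would reach that. It shows how fragile a result is, but it leaves the primary estimate where it was.

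**Conclusion.** The point holds in this form: two alpha-controlled endpoints have no listed imputation predictors, and followed as written the imputation recovers essentially nothing over complete cases. Under SD 8, ρ = 0.7 and 10–20% missing, the difference is overstated by about 0.4–0.8 mL/min/1.73 m² if low eGFR drives loss only in the bardoxolone arm. The bias is about zero if loss is random, or alike in mechanism and rate across arms, and it can go the other way. The precision cost under random loss is modest, about 3–5% in the SE.

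A reader might also infer that the plan favours bardoxolone. The documents do not support that: they give no missing rate, no on/off-treatment correlation and no pattern of loss, so neither the size nor the direction of any bias can be fixed. The simulations also leave out ACR stratum and the exposure fraction. This is an inexpensive improvement worth making, not a demonstrated error in the result.

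**What to change.** In SAP 8.5.3, 8.7.1 and 8.9.1, state that:

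- missing Week 52 (Week 104) eGFR is imputed within arm from baseline eGFR, ACR stratum, TRT_EXP1 (TRT_EXP2) and a small set of the patient's earlier post-baseline eGFR values, for example the last scheduled visits before the endpoint and, for Week 104, also Week 52;
- missing earlier visits are imputed sequentially in PROC MI;
- these earlier values are predictors only and never ANCOVA outcomes;
- the tipping-point runs use the same predictors.

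If the separate programming document already does this, one sentence in the SAP is enough.

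Two details need a decision. First, under the addendum formula, patients who stopped in Year 1 have TRT_EXP2 of at most about 336/707 = 0.48, while patients dosed in Year 2 start near 364/707 = 0.51, so imputing Week 104 for the former extrapolates. Second, some patients were already off drug at the earlier visits, and the on-to-off step estimated from the others may not apply to them. The SAP should say how both are handled.

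The cost is SAP wording, some programming and a few more imputation parameters in arms of about 78. No new data are needed.

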## 8.7.2. Sensitivity Analyses

Sensitivity analyses are included to assess the robustness of conclusions to the primary analysis of the Year 1 key secondary efficacy endpoint (i.e., change in eGFR Week 52), and to assess the assumption of MAR. The following sets of sensitivity analyses are summarized in tables and forest plots: tipping point with multiple imputation, control-based multiple imputation, and the ANCOVA model fit to the per protocol population. Additional sensitivity analyses may be performed as appropriate.

### 8.7.2.1. Tipping Point

The following tipping point sensitivity analysis is performed to assess how severe departures from MAR must be in order to overturn conclusions from the primary analysis:

1. The PROC MI procedure in SAS is applied to create 100 datasets with all missing values in the placebo group imputed based on the subjects in the placebo group. These 100 datasets will then be used for the tipping point analysis.
2. For the tipping point analysis with a shift parameter, patients in the bardoxolone methyl group with a missing value will be multiply imputed separately from the placebo-treatment arm and are assigned a shift parameter in the imputation procedure for progressively worse (lower) scores to find the point at which statistical significance is lost. Specifically, if the outcome of the hypothesis test favors bardoxolone methyl over the placebo group ( $p$ -value  $< 0.025$ ), then one point is subtracted as a shift parameter in the imputation for the bardoxolone methyl group, whilst the data for the placebo group will not be changed.
3. The ANCOVA model (see Section 8.7.1) is used to analyze each of the 100 completed data sets and PROC MIANALYZE is used to combine these results to obtain the final estimates for the given value of the shift parameter.
4. This “eGFR shifting”, as outlined in steps 2 and 3, is repeated with one shift point at a time until the hypothesis test no longer rejects the null hypothesis in favor of the bardoxolone methyl group over the placebo group (i.e. when the  $p$ -value becomes greater than 0.025). Additional increments may be used to locate the tipping point. If the result is not quite statistically significant, progressively higher scores are added to find the point at which statistical significance is attained.

### **8.7.2.2. Control-Based Multiple Imputation**

As a sensitivity analysis, all missing Week 52 eGFR values are imputed with multiple imputation using the Week 52 data from the placebo group. The control-based sensitivity analysis is performed using the ANCOVA statistical model defined in Section 8.7.1.

### **8.7.2.3. Per-Protocol Population Analysis**

The per-protocol population analysis is performed for the per-protocol population (Year 1) using the ANCOVA statistical model defined in Section 8.7.1. Missing data will not be imputed for the per-protocol population sensitivity analysis.

## **8.8. Year 2: Primary Efficacy Endpoint**

The analyses of the primary and key secondary endpoints for the Year 2 analyses are described in Sections 8.8 and 8.9. Additional details and pseudo SAS code are provided in a separate document.

### **8.8.1. Primary Analysis of the Year 2 Primary Efficacy Endpoint**

The Year 2 primary endpoint of this study is the change in eGFR at Week 100 (i.e., the end of the second year of exposure). The change from baseline in eGFR for patients treated with bardoxolone methyl is compared with placebo at Week 100 using the statistical model defined in Section 8.6.1 with the following modifications:

- The analysis uses all eGFR values collected through Week 100 according to analysis visits 0, 1, 2, 4, 6, 8, 12, 24, 36, 48, 64, 76, 88, and 100 (Section 6.5.4).
- TRT\_EXP2 is added as a covariate and TRT\_EXP1 is removed.

Inclusion of the fraction of expected two-year exposure to treatment (TRT\_EXP2; Section 6.5.11) in the MMRM model as a covariate provides an adjustment for eGFR values collected from early discontinuation patients having less than 2-years of drug exposure. All eGFR values collected in the Week 52 analysis window assess the effect following 4-weeks of drug withdrawal and therefore are not included in the MMRM analysis of Week 100.

### **8.8.2. Sensitivity Analyses**

The sensitivity analyses described in Section 8.6.2 (i.e., tipping point, control-based imputation, as-treated, and per-protocol) are performed to assess the robustness of conclusions of the 2-year primary efficacy endpoint analysis of 2-year efficacy. The per-protocol population (Year 2) is used for the per-protocol sensitivity analysis.

### **8.8.3. Summary of Sensitivity Analyses of the Primary Efficacy Endpoint – Year 2**

The following sets of sensitivity analyses are summarized in tables and forest plots: tipping point with multiple imputation, control-based imputation, MMRM fit to the as-treated population, and MMRM fit to the per protocol population.

## **8.9. Year 2: Key Secondary Endpoint**

### **8.9.1. Primary Analysis of the Year 2 Key Secondary Endpoint**

The Year 2 key secondary endpoint of this study is the change in eGFR at Week 104 (i.e., 4-weeks following the last dose after two years of drug exposure). Analysis of Week 104 assesses for retained drug benefit (relative to placebo) following withdrawal of treatment; therefore, the analysis of Week 104 data does not include eGFR values collected during treatment.

The change from baseline eGFR at Week 104 for patients treated with bardoxolone methyl are compared with placebo in a manner similar to the ANCOVA analysis of Week 52 in Year 1 (Section 8.7.1) with the following modification:

- TRT\_EXP2 is added as a covariate and TRT\_EXP1 is removed

The analysis uses eGFR values collected in the Week 104 analysis window (Section 6.5.4), which includes the follow-up assessment for patients who discontinued treatment early in the second year. Discontinuing treatment in the second year requires that patients received at least one dose of study drug in the second year. Missing Week 104 eGFR data are imputed as described in Section 8.5.3.

The difference between bardoxolone methyl and placebo in change from baseline of eGFR are estimated along with the 95% confidence interval at Week 104.

### **8.9.2. Sensitivity Analyses**

Sensitivity analyses described in Section 8.7.2 are performed to assess the robustness of conclusions of the 2-year key secondary efficacy endpoint. The following sets of sensitivity analyses are summarized in tables and forest plots: tipping point with multiple imputation, control-based multiple imputation, and the ANCOVA model fit to the per protocol population (Year 2).

## 9. EXPLORATORY EFFICACY

The following data summaries and analyses are presented for the ITT analysis set. Additional sensitivity analyses may be performed as appropriate.

All data values within the appropriate visit windows contribute to the analysis. The exception to this rule applies to any patients who begin receiving dialysis. For them, all their on-dialysis eGFR measurements are considered missing.

### 9.1. eGFR

#### 9.1.1. Continuous eGFR

Results are presented in tables with nominal significance levels for descriptive purposes only.

##### 9.1.1.1. All Available Data

Changes in eGFR for the bardoxolone methyl group compared to the placebo group are evaluated at Week 48 as the Year 1 primary endpoint, and are evaluated at Weeks 1, 2, 4, 6, 8, 12, 24, and 36 as exploratory analyses using the statistical model defined in Section 8.6.1.

Changes in eGFR for the bardoxolone methyl group compared to the placebo group are evaluated at Week 100 as the Year 2 primary endpoint, and are evaluated at Weeks 64, 76, and 88 as exploratory analyses using the statistical model defined in Section 8.8.1.

Analyses of eGFR using all available data use all eGFR values collected, irrespective of whether or not a patient is receiving treatment.

##### 9.1.1.2. As-Treated Data

To assess the effect over time of receiving bardoxolone methyl treatment, bardoxolone methyl will be compared to placebo using the statistical models defined in Section 8.6.1 (Year 1) to analyze change from baseline in eGFR values collected while receiving treatment at the on-treatment visits for Year 1 (i.e., Weeks 1, 2, 4, 6, 8, 12, 24, 36, 48). Similarly, the statistical models defined in Section 8.8.1 (Year 2) will be used to analyze change from baseline in eGFR values collected while receiving treatment through the on-treatment visits in Year 2 (i.e., 64, 76, 88, and 100).

eGFR values collected 14 days or more after the last dose of study drug will be excluded from the as-treated analysis.

